11.1.4 Response Criteria

11.1.4.1 Evaluation of Target Lesions

Complete Response (CR): Disappearance of all target lesions. Any pathological lymph nodes (whether target or non-target) must have reduction in short axis to <10 mm.

Partial Response (PR): At least a 30% decrease in the sum of the diameters of target lesions, taking as reference the baseline sum diameters.

Progressive Disease (PD): At least a 20% increase in the sum of the diameters of target lesions, taking as reference the smallest sum on study (this includes the baseline sum if that is the smallest on study). In addition to the relative increase of 20%, the sum must also demonstrate an absolute increase of at least 5 mm. (Note: the appearance of one or more new lesions is also considered progressions).

Stable Disease (SD): Neither sufficient shrinkage to qualify for PR nor sufficient increase to qualify for PD, taking as reference the smallest sum diameters while on study.

11.1.4.2 Evaluation of Non-Target Lesions

Complete Response (CR): Disappearance of all non-target lesions and normalization of tumor marker level. All lymph nodes must be non-pathological in size (<10 mm short axis).

Note: If tumor markers are initially above the upper normal limit, they must

normalize for a patient to be considered in complete clinical response.

Non-CR/Non-PD: Persistence of one or more non-target lesion(s) and/or maintenance of tumor marker level above the normal limits.

Progressive Disease (PD): Appearance of one or more new lesions and/or *unequivocal progression* of existing non-target lesions. *Unequivocal progression* should not normally trump target lesion status. It must be representative of overall disease status change, not a single lesion increase.

Although a clear progression of “non-target” lesions only is exceptional, the opinion of the treating physician should prevail in such circumstances, and the progression status should be confirmed at a later time by the review panel (or Principal Investigator).

11.1.4.3 Evaluation of New Lesions

The finding of a new lesion should be unequivocal (i.e. not due to difference in scanning technique, imaging modality, or findings thought to represent something other than tumor (for example, some ‘new’ bone lesions may be simply healing or flare of pre-existing lesions). However, a lesion identified on a follow-up scan in an anatomical location that was not scanned at baseline is considered new and will indicate PD. If a new lesion is equivocal (because of small size etc.), follow-up evaluation will clarify if it truly represents new disease and if PD is confirmed, progression should be declared using the date of the initial scan on which the lesion was discovered.

11.1.4.4 Evaluation of Best Overall Response

The best overall response is the best response recorded from the start of the treatment until disease progression/recurrence (taking as reference for progressive disease the smallest measurements recorded since the treatment started). The patient's best response assignment will depend on the achievement of both measurement and confirmation criteria.

For Participants with Measurable Disease (i.e., Target Disease)

Target Lesions	Non-Target Lesions	New Lesions	Overall Response	Best Overall Response when Confirmation is Required*
CR	CR	No	CR	≥ 4 wks Confirmation**
CR	Non-CR/Non-PD	No	PR	
CR	Not evaluated	No	PR	
PR	Non-CR/Non-PD/not evaluated	No	PR	

SD	Non-CR/Non-PD/not evaluated	No	SD	Documented at least once ≥ 4 wks from baseline**
PD	Any	Yes or No	PD	no prior SD, PR or CR
Any	PD***	Yes or No	PD	
Any	Any	Yes	PD	

* See RECIST 1.1 manuscript for further details on what is evidence of a new lesion. ** Only for non-randomized trials with response as primary endpoint. *** In exceptional circumstances, unequivocal progression in non-target lesions may be accepted as disease progression.
 
Note: Participants with a global deterioration of health status requiring discontinuation of treatment without objective evidence of disease progression at that time should be reported as “symptomatic deterioration.” Every effort should be made to document the objective progression even after discontinuation of treatment.
				

For Participants with Non-Measurable Disease (i.e., Non-Target Disease)

Non-Target Lesions	New Lesions	Overall Response
CR	No	CR
Non-CR/non-PD	No	Non-CR/non-PD*
Not all evaluated	No	not evaluated
Unequivocal PD	Yes or No	PD
Any	Yes	PD

* ‘Non-CR/non-PD’ is preferred over ‘stable disease’ for non-target disease since SD is increasingly used as an endpoint for assessment of efficacy in some trials so to assign this category when no lesions can be measured is not advised
		

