5.4 General Concomitant Medication and Supportive Care Guidelines

5.4.1 Concomitant Medications Guidelines

Medications or vaccinations specifically prohibited in the exclusion criteria are not allowed during the ongoing trial. If there is a clinical indication for one of these or other medications or

vaccinations specifically prohibited during the trial, discontinuation from trial therapy or vaccination may be required. The investigator should discuss any questions regarding this with the overall PI.

Acceptable Concomitant Medications

All treatments that the investigator considers necessary for a subject's welfare may be administered at the discretion of the investigator in keeping with the community standards of medical care and documented in the medical record. Selected medications of interest received within 28 days before the first dose of trial treatment and 30 days after the last dose of trial treatment, including dosage, frequency, route, and dates of administration will be recorded.

Concurrent use of somatostatin analogs is allowed, provided that the patient has been on a stable dose for at least two months.

Concomitant medications that are known to prolong the QTcF interval and should be used with caution in subjects who receive cabozantinib until they have permanently discontinued cabozantinib treatment (refer to <http://www.qtdrugs.org> for a list of drugs which have the potential to prolong the QTcF interval).

Drugs known to be P-glycoprotein substrates (e.g. fexofenadine, aliskiren, ambrisentan, digoxin, colchicine, maraviroc, posaconazole, tolvaptan, etc.) should be used with caution as cabozantinib can cause increased P-glycoprotein substrate plasma concentrations.

MRP2 inhibitors such as cyclosporine, delavirine, efavirenz, and emtricitabine should be used with caution during treatment with cabozantinib as coadministration can cause increased cabozantinib plasma concentrations.

Highly protein-bound medications (e.g. diazepam, furosemide, dicloxacillin, propranolol, etc.) should be used with caution during treatment with cabozantinib.

Bisphosphonates should be used with caution due to the nephrotoxic potential and potential for osteonecrosis of the jaw previously described in association with these agents.

Prohibited Concomitant Medications

Subjects are prohibited from receiving the following therapies during the Screening and Treatment Phase of this trial:

- Antineoplastic systemic chemotherapy or biological therapy

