5.6 Duration of Follow Up

Participants will be followed for initiation of a new regimen of anti-neoplastic therapy, first disease progression event after removal from protocol therapy or until death . Tumor assessments should continue to be performed every 12 weeks on these participants until first disease progression event or until death, whichever occurs first.

Participants removed from protocol therapy for unacceptable adverse event(s) will be followed until resolution or stabilization of the adverse event.

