11.2.6 Immune-Related Best Overall Response Using irRC (irBOR)

irBOR is the best confirmed overall response over the study as a whole, recorded between the date of first dose until the last tumor assessment before subsequent therapy (except for local palliative radiotherapy for painful bone lesions) for the individual subject in the study. For the assessment of irBOR, all available assessments per subject are considered.

irCR or irPR determinations included in the irBOR assessment must be confirmed by a second (confirmatory) evaluation meeting the criteria for response and performed no less than 4 weeks after the criteria for response are first met.

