16 STATISTICAL CONSIDERATIONS

16.1 Study Design/Endpoints

The study intends to examine the clinical efficacy and tolerability of cabozantinib and nivolumab in the treatment of patients with advanced carcinoid. The study includes an interim analysis after 18 patients to assure tolerability and to evaluate response rate of combining cabozantinib and nivolumab. This combination is likely to be well tolerated based on prior studies in patients with breast cancer and renal cell carcinoma, but these data require confirmation in patients with carcinoid tumors. This is a one-arm study without randomization. If objectives of the interim analysis are met then enrollment will be expanded to include 17 additional patients.

16.1.1 Primary endpoint:

The primary efficacy endpoint is the objective response rate (ORR) in patients with advanced carcinoid tumors treated with the combination of cabozantinib and nivolumab. ORR is defined using the RECIST 1.1 criteria as the proportion of subjects with a confirmed CR or a confirmed PR.

16.1.2 Secondary endpoint:

The secondary endpoints are safety, response rate according to immune-related response criteria, duration of response, progression free survival (PFS), and overall survival (OS) for patients with advanced carcinoid tumors treated with the combination of cabozantinib and nivolumab.

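### The RECIST best-response window closes only at progression, so a confirmed response on a later anticancer treatment, in a patient who left without progressing, would count in the primary ORR

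*Combined protocol and SAP*

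**What the plan says.** **Primary endpoint.** Section 16.1.1 states: "ORR is defined using the RECIST 1.1 criteria as the proportion of subjects with a confirmed CR or a confirmed PR". The window comes from Section 11.1.4.4: "The best overall response is the best response recorded from the start of the treatment until disease progression/recurrence". Response must be confirmed at least 4 weeks later (Sections 11.1 and 11.1.4.4), but neither section says that the confirming scan must precede any new treatment. The analysis plan in Section 16.3 adds no cut-off.

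**Secondary irRC endpoint.** Under Section 11.2.6 the best irRC response is the one "recorded between the date of first dose until the last tumor assessment before subsequent therapy", with an exception for local palliative radiotherapy to painful bone lesions. Section 16.3 analyses the irRC rate by the same method as the ORR.

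**After protocol therapy.** Section 5.5 lists several exits that do not involve progression, among them adverse events, intercurrent illness, non-compliance and withdrawal from therapy. Section 5.6 opens with "Participants will be followed for initiation of a new regimen of anti-neoplastic therapy", alongside progression and death, and then says: "Tumor assessments should continue to be performed every 12 weeks on these participants until first disease progression event or until death, whichever occurs first". Section 5.7 does not make the start of new therapy a reason to come off study. The concomitant-medication ban in Section 5.4.1 is limited in time: "Subjects are prohibited from receiving the following therapies during the Screening and Treatment Phase of this trial".

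**The concern.** The primary objective is the activity of the combination. A response first seen after a patient has moved to another treatment says little about the combination, yet the RECIST rule has no means of excluding it. The protocol contains such a cut-off, but only for the secondary irRC endpoint. A patient who stops for toxicity with stable disease, changes treatment and then shrinks by 30% from baseline, with confirmation, would be a responder for the primary endpoint; the same scans would be ignored for irRC.

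The error can only add responses. The decision rests on a small count: 6/35 (17.1%) fails and 7/35 (20.0%) succeeds, so one response, 1/35 = 2.9 percentage points, can decide the trial.

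**Working it through.** **1. Can the case arise under the text?** Each step is open:
- Leaving without progression: Section 5.5 lists the routes.
- Starting another treatment: the ban in Section 5.4.1 covers screening and treatment, not follow-up. Section 2.1 names other options for this disease.
- Being scanned afterwards: the scan sentence in Section 5.6 stops at progression or death only.
- Counting: Section 11.1.4.4 admits any response before progression, and the confirming scan may also fall on the later treatment.

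**2. The plan's own figure.** Section 16.2 gives: continue if at least 3 of 18 respond; declare success if at least 7 of 35 respond; null rate 10%; exact alpha 0.047.

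α = Σ (x = 3 to 18) P[Bin(18, 0.10) = x] × P[Bin(17, 0.10) ≥ 7 − x] = 0.0474

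This reproduces the stated value. The margin below 5% is about 0.3 percentage points.

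**3. Effect of later-treatment responses.** The inputs below are assumptions; none is in the documents.
- m = number of the 35 who leave without progression, split evenly between the stages: 4 or 8.
- w = share of those who start another treatment before progressing: one half or all.
- r = confirmed response rate on that treatment: 10% or 20%.
- Late responses count in the final total but not at the stage 1 gate, since they need an exit, a new treatment, a scan and a confirmation.

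The true response rate to the combination stays at 10%. Let X1 be the stage 1 responses to the combination, distributed Bin(18, 0.10), with X1 ≥ 3 required. Each stage 1 leaver who has not responded adds a late response with probability w·r; call their total L1. In stage 2, 17 − m/2 patients respond with probability 0.10, and m/2 with probability 1 − 0.90(1 − w·r); call their total X2. Success is X1 ≥ 3 together with X1 + L1 + X2 ≥ 7.

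| m | r | Type I error, half switch | Type I error, all switch |
|---|---|---|---|
| 4 | 10% | 0.057 | 0.066 |
| 4 | 20% | 0.066 | 0.086 |
| 8 | 10% | 0.066 | 0.087 |
| 8 | 20% | 0.087 | 0.130 |

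The expected number of added responses is m × 0.90 × w·r. It runs from 4 × 0.90 × 0.05 = 0.18 to 8 × 0.90 × 0.20 = 1.44 if all 35 patients are enrolled.

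**4. A low case.** If 5% of non-responders switch before progressing and 5% of those respond, the apparent ORR is 0.10 + 0.90 × 0.05 × 0.05 = 0.102. Type I error is then 0.051 (late responses in the final count only) or 0.052 (also at the gate).

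**The case against.** **Section 5.6 can be read the other way.** Its opening sentence may list three alternative ends of follow-up, with a new regimen as one of them. The scan sentence would then cover only patients still followed, and few or no protocol scans would come after a switch. The study calendar has no long-term tumour-assessment column to settle this. The ambiguity stands. It does not remove the gap, because the scan sentence names only progression or death, and neither sentence limits which scans may enter best response.

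**The route is narrow.** The patient must leave without RECIST progression, start another treatment, shrink by at least 30% from the original baseline and be confirmed, all before progressing. This stands. A reader might infer that any response to a later treatment counts. It does not: responses after RECIST progression are already outside the window. The documents also do not direct anyone to credit later treatments; they permit it by silence.

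**The effect may be small.** This stands too. A reader might quote a type I error of 0.072 to 0.186. That range comes from the same values of m and r, but makes every leaver switch before progression and lets late responses open the stage 1 gate. A reader might also quote 0.094 or 0.111; those figures suppose that one misattributed response, in stage 2 or stage 1 respectively, has certainly occurred. They are not operating characteristics of the design. The documents support none of these figures as an estimate.

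**The two windows differ anyway.** The irRC window has no stop at progression and allows palliative bone radiotherapy. The comparison with Section 11.2.6 therefore shows only that the subsequent-therapy cut-off is missing from the primary endpoint. It does not show that the two rates were meant to cover the same period.

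**Conclusion.** The gap is real and concerns the primary endpoint. As written, a confirmed response reached on another treatment counts towards the ORR if the patient left protocol therapy without progressing and has not progressed since. Any resulting bias in the ORR is upward.

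Its size cannot be estimated from the documents. Under the assumptions shown, type I error goes from 0.047 to about 0.057 to 0.130. With very few switches it stays near 0.05. These figures are a sensitivity range, not a forecast. The change is still worth making, because the design has little room below 5% and one response can decide the outcome.

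**What to change.** In Sections 11.1.4.4 and 16.1.1, state that best overall response uses assessments up to the earlier of RECIST progression or the start of subsequent anticancer therapy, whether systemic or local to target lesions. Carry over the Section 11.2.6 exception for palliative bone radiotherapy. Require the confirming scan to fall before the same date. Patients without a confirmed response by then stay in the denominator as non-responders.

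In Section 5.6, say plainly whether scans continue after a new regimen starts. Any such scans can still serve time-to-event follow-up.

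This aligns the subsequent-therapy cut-off with Section 11.2.6, although the RECIST and irRC windows will still differ on progression. The cost is a sentence in each place. The start of a new regimen is already followed under Section 5.6; the case report form should also capture the date of any local treatment to target lesions. No extra visits or scans are needed. The downside is that the reported ORR may be slightly lower.

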11.1.5 Duration of Response

Duration of overall response: The duration of overall response is measured from the time measurement criteria are met for CR or PR (whichever is first recorded) until the first date that recurrent or progressive disease is objectively documented (taking as reference for progressive disease the smallest measurements recorded since the treatment started, or death due to any cause. Participants without events reported are censored at the last disease evaluation).

Duration of overall complete response: The duration of overall CR is measured from the time measurement criteria are first met for CR until the first date that progressive disease is objectively documented, or death due to any cause. Participants without events reported are censored at the last disease evaluation.

Duration of stable disease: Stable disease is measured from the start of the treatment until the criteria for progression are met, taking as reference the smallest measurements recorded since the treatment started, including the baseline measurements.

11.1.6 Survival and Time to Progression Definitions

Overall Survival: Overall Survival (OS) is defined as the time from randomization (or registration) to death due to any cause, or censored at date last known alive.

Progression-Free Survival: Progression-Free Survival (PFS) is defined as the time from randomization (or registration) to the earlier of progression or death due to any cause. Participants alive without disease progression are censored at date of last disease evaluation.

Time to Progression: Time to Progression (TTP) is defined as the time from randomization (or registration) to progression, or censored at date of last disease evaluation for those without progression reported.

11.2 Other Response Parameters

11.2.1 Definition of Tumor Response Using Immune-Related Response Criteria (irRC)

The sum of the longest diameter of lesions (SPD) at tumor assessment using the immune-related response criteria (irRC) for progressive disease incorporate the contribution of new measurable lesions. Each net Percentage Change in Tumor Burden per assessment using irRC criteria accounts for the size and growth kinetics of both old and new lesions as they appear.

11.2.2 Impact of New Lesions on irRC

New lesions in and of themselves do not qualify as progressive disease. However, their contribution to total tumor burden is included in the SPD which in turn feeds into the irRC criteria for tumor response. Therefore, new non-measurable lesions will not discontinue any subject from the study.

11.2.3 Definition of Target Lesions Response Using irRC

- . **irComplete Response (irCR):** Complete disappearance of all target lesions. This category encompasses exactly the same subjects as “CR” by the mWHO criteria.
- . **irPartial Response (irPR):** Decrease, relative to baseline, or 50% or greater in the sum of the products of the two largest perpendicular diameters of all target and all new measurable target lesions (i.e., Percentage Change in Tumor Burden). Note: the appearance of new measurable lesions is factored into the overall tumor burden, but does not automatically qualify as progressive disease until the SBD increases by >25% when compared to SPD at nadir.
- . **irStable Disease (irSD):** Does not meet criteria for irRC or irPR, in the absence of progressive disease.
- . **irProgressive Disease (irPD):** At least 25% increase Percentage Change in Tumor Burden (i.e. taking SPD of all target lesions and any new lesions) when compared to SPD at nadir.

11.2.4 Definition of Non-Target Lesions Response Using irRC

- **irComplete Response (irCR):** Complete disappearance of all non-target lesions. This category encompasses exactly the same subjects as “CR” by the mWHO criteria.
- **irPartial Response (irPR) or irStable Disease (irSD):** Non-target lesion(s) are not considered in the definition of PR; these terms do not apply.
- **irProgressive Disease (irPD):** Increases in number or size of non-target lesion(s) does not constitute progressive disease unless/until the Percentage Change in Tumor Burden increases by 25% (i.e. the SPD at nadir of the target lesions increases by the required amount).

11.2.5 Definition of Overall Response Using irRC

Overall response using irRC will be based on these criteria:

- **Immune-Related Complete Response (irCR):** Complete disappearance of all tumor lesions (target and non-target) together with no new measurable/unmeasurable lesions for at least 4 weeks from the date of documentation of complete response.
- **Immune-Related Partial Response (irPR):** The sum of the products of the two largest perpendicular diameters of all target lesions is measured and captured as the SPD baseline. At each subsequent tumor assessment, the SPD of the two largest perpendicular diameters of all target lesions and of new measurable lesions are added together to provide the Immune Response Sum of Product Diameters (irSPD). A decrease, relative to baseline, of the irSPD compared to the previously SPD baseline of 50% or greater is considered an irPR.
- **Immune-Related Stable Disease (irSD):** irSD is defined as the failure to meet criteria for immune complete response or immune partial response, in the absence of progressive disease
- **Immune-Related Progressive Disease (irPD):** It is recommended in difficult cases to confirm PD by serial imaging. Any of the following will constitute PD:
 - At least 25% increase in the SPD of all target lesions over baseline SPD calculated for the target lesions.
 - At least 25% increase in the SPD of all target lesions and new measurable lesions (irSPD) over the baseline SPD calculated for the target lesions.

Criteria for determining overall response by irRC are summarized as follows:

Immune-Related Response Criteria Definitions

Target Lesion Definition	Non-Target Lesion Definition	New Measurable Lesions	New Unmeasurable Lesions	Percent change in tumor burden (including measurable new lesions when present)	Overall irRC Response
Complete Response	Complete Response	No	No	-100%	irCR
Partial Response	Any	Any	Any	$\geq -50\%$	irPR
				$<-50\% \text{ to } <+25\%$	irSD
				$>+25\%$	irPD
Stable Disease	Any	Any	Any	$<-50\% \text{ to } <+25\%$	irSD
				$>+25\%$	irPD
Progressive Disease	Any	Any	Any	$\geq +25\%$	irPD

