5.5 Criteria for Taking a Participant Off Protocol Therapy

Duration of therapy will depend on individual response, evidence of disease progression and tolerance. In the absence of treatment delays due to adverse event(s), treatment may continue for indefinite number or until one of the following criteria applies:

1. Disease progression by RECIST 1.1 Criteria
Although the primary endpoint is ORR as defined by RECIST 1.1, patients may remain on protocol therapy until the time of disease progression by irRC criteria. The immune criteria allows treatment beyond initial radiographic worsening of disease in order to distinguish between pseudoprogression and true disease progression.
2. Participants who have attained a confirmed complete response (CR) and who have been treated for at least 24 weeks on protocol therapy and had at least four treatments with nivolumab beyond the date when the initial CR was declared. Participants who stop nivolumab with CR may be eligible for additional nivolumab therapy if they progress after stopping study treatment. This retreatment is termed the Second Course Phase Therapy, as summarized below.
3. Intercurrent illness that prevents further administration of treatment
4. Unacceptable adverse event(s). If the subject does not recover from his or her toxicities to tolerable Grade ≤ 2 within 6 weeks, the subject will have study treatment discontinued unless there is unequivocal evidence that the subject is benefitting. In this situation, a subject may be able to restart therapy with a dose reduction upon resolution of the toxicity and with agreement of the principal investigator / Sponsor.
5. Participant demonstrates an inability or unwillingness to comply with the oral medication regimen and/or documentation requirements. OR Significant noncompliance with the protocol schedule in the opinion of the investigator. OR Subjects who cannot tolerate the minimum protocol-specified dose of study treatment will have study treatment discontinued.
6. Participant decides to withdraw from the protocol therapy
7. General or specific changes in the participant's condition render the participant unacceptable for further treatment in the judgment of the treating investigator

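### Progression by irRC is measured from nadir in sections 11.2.3 and 11.2.4 but from baseline in 11.2.5; for a tumour burden that has halved, irPD falls at +25% or at +150% regrowth

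*Combined protocol and SAP*

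**What the plan says.** All references are to the combined protocol and SAP.

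- **5.5 item 1.** RECIST 1.1 progression ends protocol therapy, with an exception: "patients may remain on protocol therapy until the time of disease progression by irRC criteria". The stated purpose is to tell pseudoprogression from true progression.
- **11.2.3, irPD definition.** A 25% increase, "taking SPD of all target lesions and any new lesions) when compared to SPD at nadir".
- **11.2.3, note under irPR.** A new measurable lesion "does not automatically qualify as progressive disease until the SBD increases by >25% when compared to SPD at nadir".
- **11.2.4, non-target lesions.** Progression only if "the SPD at nadir of the target lesions increases by the required amount".
- **11.2.5, overall response.** Two irPD bullets, either one sufficient. The first is "At least 25% increase in the SPD of all target lesions over baseline SPD calculated for the target lesions". The second applies the same 25% over baseline SPD to target plus new measurable lesions (irSPD).
- **11.2.5, table.** The column "Percent change in tumor burden (including measurable new lesions when present)" names no reference point.

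irPR is a decrease of 50% or more from baseline in both 11.2.3 and 11.2.5.

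**The concern.** Three statements use nadir and two use baseline, essentially for the same quantity: 11.2.3 already counts new lesions with the target lesions, as the second bullet of 11.2.5 does. The two references coincide only if SPD never fell below baseline. They diverge in patients whose tumours shrank, and the gap widens with the depth of shrinkage.

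Because irRC progression is the imaging limit of therapy beyond RECIST progression, two investigators could each follow the protocol on the same scan and reach opposite decisions about stopping. Under the baseline reference, regrowth of target lesions after a response can be substantial before irPD is reached, which fits poorly with an exception meant for pseudoprogression.

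**Working it through.** The plan states no figure for this, so the check is arithmetic on its thresholds.

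**Inputs.** irPD at +25% (11.2.3 to 11.2.5); irPR at -50% from baseline (11.2.3, 11.2.5). Let n = nadir SPD / baseline SPD.

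**Where the rules disagree.** The nadir rule calls irPD at 1.25n × baseline, the baseline rule at 1.25 × baseline. Between the two, the calls conflict. Regrowth from nadir needed under the baseline rule is 1.25/n - 1.

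| n | irPD by nadir rule (× baseline) | Regrowth needed, nadir rule | Regrowth needed, baseline rule |
|---|---|---|---|
| 1.00 | 1.25 | +25% | +25% |
| 0.70 | 0.875 | +25% | +79% |
| 0.50 | 0.625 | +25% | +150% |
| 0.30 | 0.375 | +25% | +317% |

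**Example.** SPD falls to 0.50 of baseline and regrows to 0.90. From nadir: 0.90/0.50 - 1 = +80%, irPD. From baseline: 0.90 - 1 = -10%, not irPD.

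**Does the 11.2.5 table settle it?** It places -50% and +25% on one percent-change scale. Since -50% is relative to baseline, the natural reading is baseline throughout. Take n = 0.50 regrown to 0.625. Target status is progressive disease under 11.2.3, but the change from baseline is 0.625 - 1 = -37.5%. The Progressive Disease row requires at least +25%, and the other rows require a different target status. The patient fits no row and meets neither irPD bullet.

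**Relation to RECIST progression (illustration).** Take a responder at exactly -30%, with both diameters of each lesion changing in proportion (so n = 0.70² = 0.49) and a baseline target sum of 36 mm. RECIST progression needs +20% over the smallest sum, and "the sum must also demonstrate an absolute increase of at least 5 mm" (11.1.4.1).

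- RECIST progression: the larger of 0.84 × 36 = 30.24 mm and 25.2 + 5 = 30.2 mm, so 30.24 mm.
- irPD by the baseline rule: √1.25 × 36 = 1.118 × 36 = 40.25 mm, a further 40.25/30.24 - 1 = +33%.
- Below a baseline sum of 5/(1.118 - 0.70) = 12.0 mm the order reverses, and irPD by baseline comes before RECIST progression.
- irPD by the nadir rule: +11.8% in diameter for proportional growth, before RECIST's +20%; +25% if only one diameter grows, after it.

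**Overlap under a nadir rule.** One scan meets both irPR and irPD when 1.25n ≤ 0.50, that is n ≤ 0.40. Example: n = 0.30 regrown to 0.45 is -55% from baseline and 0.45/0.30 - 1 = +50% from nadir. A precedence rule is therefore needed.

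**Why one bullet rather than two.** Constructed case: baseline SPD 2,000 mm²; then targets 1,000 + new 600 = 1,600; then targets 1,300 + new 200 = 1,500. A target-only nadir bullet calls irPD (1,300/1,000 = +30%) while total burden is falling. That would contradict 11.2.1, where net change covers old and new lesions together. A single bullet on total irSPD avoids this.

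**The case against.** The best defence is that the sections form a hierarchy. 11.2.3 and 11.2.4 grade target and non-target lesions, 11.2.5 alone gives the overall call, and irRC progression in 5.5 most naturally means that overall call. The operating rule would then be baseline, and the table's common scale supports this. That is a fair reading, but it does not remove the conflict: 11.2.3 counts new lesions too, target status feeds the table, and the patient at 0.625 of baseline still has no row.

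A second objection is that choosing nadir is a treatment-policy choice, since aligning 11.2.3 and 11.2.4 to baseline would also end the conflict. This stands in part. The documents do not say which reference was intended. Nadir has the support of three irRC statements and of the protocol's own RECIST rule, which takes the smallest sum on study. A sponsor who prefers baseline would still have to amend 11.2.3 and 11.2.4.

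Third, the consequence is limited. Continuation is permitted rather than required, and 5.5 item 7 lets the investigator stop on clinical judgment. That stands.

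A reader might infer that most responders would stay on both drugs well past RECIST progression. The documents do not support this: they give no distribution of target sums, nadirs or modes of progression, and the +33% above rests on one assumed case. Nor does an expected number of responders among the 35 patients measure how many are affected. Not every responder regrows on therapy, and patients with shrinkage short of a response are exposed as well.

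**Conclusion.** The irPD reference is wrong as written: two incompatible rules are in force and nothing ranks them. For SPD that has halved, irPD falls at +25% or at +150% regrowth from nadir. These figures follow from the stated thresholds alone; only the comparison with RECIST progression assumes a particular shrinkage, lesion size and growth pattern.

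The effect is on permitted treatment duration and on irPD/irSD calls in patients who shrink and then regrow on therapy. How many that will be cannot be derived from the documents.

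A reader might infer that the efficacy conclusion is at risk. It is not: the primary response rate, the go/no-go rule and RECIST progression-free survival use RECIST 1.1, which has its own definition of progression. A reader might equally infer that the irRC response rate is wholly untouched. That is too strong. irPR is relative to baseline in both sections, and 11.2.6 considers all available assessments, so there is no direct effect. But the reference limits how long therapy continues, so a late irPR could differ. The effect is indirect and probably small.

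The text should be corrected, but the point does not threaten the trial's main result.

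**What to change.** 1. In 11.2.5, replace both irPD bullets with one: *irSPD (target plus new measurable lesions) at least 25% above the smallest irSPD recorded on study, the baseline SPD included.*
2. Use the same nadir wording in 11.2.3 and 11.2.4.
3. In the 11.2.5 table, label irPD *≥ +25% from nadir irSPD*, keep irCR and irPR relative to baseline, and define irSD as none of these.
4. Add: *An assessment that meets both irPR (from baseline) and irPD (from nadir) is irPD for the 5.5 stopping rule; for irBOR, whether it confirms an earlier irPR under 11.2.6 is judged only by the 50% decrease from baseline.*
5. In 5.5 item 1, after the reference to irRC progression, add *(overall irPD, section 11.2.5)*.

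The cost is an amendment of text, with no new scan, procedure or patient. It does have a clinical consequence: some responders reach the irRC limit earlier than under the baseline wording, and for proportional target regrowth the exception adds little or no time beyond RECIST progression. It still covers RECIST progression caused by new lesions, since 11.2.2 says "New lesions in and of themselves do not qualify as progressive disease". For example, if target SPD stays at a nadir of 2,000 mm² and one 15 × 15 mm lesion appears, irSPD rises by 225/2,000 = 11%, which is not irPD.
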